4.3 JUSTIFICATION FOR INTERVENTION

COPD is an under-recognized epidemic in older Americans. Research priorities of NIA and AGS identify a critical need for GeriPal models. However, GeriPal integration is rare in COPD, and no GeriPal interventions have been systematically developed and tested in community-dwelling older adults with COPD. This study is innovative in the following ways: **First**, the ENABLE model for early, concurrent palliative care in oncology is successful in patients with advanced cancer to improved quality of life and survival. **Second**: EPIC’s palliative nurse coaches guide both patients and their caregivers, and its telephone delivery model is primed to reach isolated older adults from rural settings. **Third**, eligibility will not be limited to end-stage COPD as in other studies; instead, we will include participants with less severe COPD who also have significant COPD symptoms such as breathlessness, use oxygen, or have been hospitalized in the prior year, which are associated with high emotional burden and reduced and

quality of life in adults with COPD. **Fourth**, our multiphase study is the first to use Baltes' Theory of Successful Aging to refine the geriatrics content of ENABLE to meet specific care needs of the old-old. **Fifth**, we will measure critical data on feasibility, acceptability, and GeriPal secondary outcomes to inform the R01.

4.4 END-OF-STUDY DEFINITION

Participants are considered to have completed the study if they have completed week 24 questionnaires.

5 STUDY POPULATION

5.1 INCLUSION CRITERIA

In order to be eligible to participate in this study, potential participants must meet all of the following criteria:

Patient Participant Inclusion Criteria (must meet all of the following):

1. ≥ 60 years;
2. COPD on routinely collected spirometry ($FEV_1/FVC < 0.70$ + $FEV_1 < 80\%$);
3. Able to speak English;
4. At least one of the following:
 - o 4a) Severe breathlessness as defined by a documented modified Medical Research Council (mMRC) Dyspnea Scale Score > 2 in the medical record or any of the following levels of severe breathlessness by medical review: breathless after walking about 100 yards, breathless after a walking few minutes on level ground, or too breathless to leave the house or when dressing); OR,
 - o 4b) ≥ 1 hospitalization in the year prior but > 30 days from enrollment; OR,
 - o 4c) On supplemental oxygen (exertional or continuous).

Caregiver Participant Inclusion criteria:

1. ≥ 18 years;
2. Self-reporting as "an unpaid spouse or caregiver, relative, or friend who knows [the patient] well and is involved in their medical care";
3. Able to speak English.

5.2 EXCLUSION CRITERIA

An individual who meets any of one of the following criteria will be excluded from participation in this study:

Patient Participant Exclusion Criteria (can be excluded for ANY of the following):

1. No access to a dedicated telephone service;
2. Recent hospitalization for any reason or exacerbation of COPD in the past 30 days or ongoing exacerbation symptoms requiring treatment with antibiotics and steroids;
3. Treated within the past 60 days for an advanced cancer defined as metastatic and/or recurrent/progressive stage III/IV cancer, including brain, lung, breast, gynecologic, head and neck, gastrointestinal, genitourinary cancer, and hematologic malignancies by self report or chart review;
4. Active schizophrenia, major depressive disorder, bipolar disorder, suicidal ideations, or substance abuse by self-report or chart review (Active means currently being treated for schizophrenia, bipolar disorder, or suicidal ideations or having active and untreated major depressive disorder, i.e. not under the care of a clinician or not on medications such as antidepressants or mood stabilizers, or having active and untreated substance abuse, i.e. not on medication or enrolled in a substance abuse program)
5. Non-correctable hearing impairment (i.e. hearing impairment despite hearing aids);
6. Severe cognitive impairment (score ≤ 3 points on 6-item Callahan Screener): a) Correctly identify current year (1 point); b) Correctly identify current month (1 point); c) Correctly identify current day (1 point); d) Correctly recall "apple" after 5 minutes (1 point); e) Correctly recall "table" after 5 minutes (1 point); f) Correctly recall "penny" after 5 minutes (1 point)

Caregiver Exclusion Criteria:

1. No access to a dedicated telephone service;
2. Active schizophrenia, major depressive disorder, bipolar disorder, suicidal ideation, or substance abuse by self-report (Active schizophrenia, major depressive disorder, bipolar disorder, suicidal ideation, or substance abuse by self-report or chart review (Active means currently being treated for schizophrenia, bipolar disorder, or suicidal ideations or having active and untreated major depressive disorder, i.e. not under the care of a clinician or not on medications such as antidepressants or mood stabilizers, or having active and untreated substance abuse, i.e. not on medication or enrolled in a substance abuse program)
3. Non-correctable hearing impairment (i.e. hearing impairment despite hearing aids);
4. Severe cognitive impairment (score ≤ 3 points on a 6-item Callahan screener): a) Correctly identify current year (1 point); b) Correctly identify current month (1 point); c) Correctly identify current day (1 point); d) Correctly recall "apple" after 5 minutes (1 point); e) Correctly recall "table" after 5 minutes (1 point); f) Correctly recall "penny" after 5 minutes (1 point)

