expresses suicidal ideation to the nurse coach or study coordinator. During normal business hours the participant will be immediately referred to the PI so that he may perform a risk assessment and develop an appropriate management plan with the participant. In the event the PI is not available, the participant will be immediately referred to Emergency Psychiatric Services Department which is available 24 hours/day, 7 days/week.

Regarding risks related to loss of confidentiality, all participants' contact information will be stored in the password protected REDCap database that exists within the firewalled network of the School of Medicine and School of Nursing. Each participant will be assigned an identification number so that survey data will not be labeled with the participant's name. All paper data will be stored in locked cabinets and password protected computers within the offices and laboratories at the School of Nursing. Only study personnel will be allowed to access the data. Transcripts from interviews will be reviewed by the PI and identifiable information such as names and places will be removed from the transcript. Post-intervention interviews of participants who completed the intervention arm will be conducted by the PI or trained study coordinator in their private offices to minimize any risk of overheard conversations. The study coordinator will ask participants if this is a good time to talk and will remind the participant that the interviews are audio recorded and transcribed. The study coordinator will allow the participant to skip any questions if needed. The electronic audio file will be stored on a password-protected computer by the study coordinator and uploaded to the secure website of Landmark Associates for verbatim transcription.

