The primary risks of study participation are a loss of confidentiality and the discomfort associated with discussing aspects of one's experience coping with advanced cancer. To address these concerns, [name] will train all project staff to recognize signs of distress and to be supportive and/or make alternative plans for completing study-related tasks at a later date, if necessary. If a participant exhibits suicidal ideation at any point, [name] and other key clinical members of the study team will be contacted immediately to implement a crisis intervention plan (see **Section 12.2** for Emotional Distress/Suicide Protocol).

Plans to Monitor Trial Performance (e.g., assure fidelity to protocol and integrity of data)

[name] and [name] have developed and utilized structured processes for ensuring fidelity in study protocols including: 1) core training and study-specific refresher course in standardized interviewing that includes role-playing and supervision; 2) weekly team meetings to troubleshoot recruitment and data collection issues; and, 3) use of data entry software that provides entry validation range tests and is designed to minimize missing data by flagging missed items before surveys are submitted.

A data analyst study team member will manually extract data from the medical record regarding patient participants' clinical characteristics of stage, treatment, and co-morbidities. To ensure accuracy, the analyst will audit a random 10% of the medical records to verify the accuracy of the abstracted

information. The study coordinator will maintain and monitor the database regularly throughout the study. The database is password-protected and sits behind the firewall of UAB.

Interim Analyses and Stopping Rules

Early Termination for Significant Risk or Injury. - This is unlikely due to the supportive, non-invasive nature of the intervention. However, we will summarize adverse event data annually to the SO for consideration of study continuation. The study design does not include planned interim analyses to identify the need to stop early due to significant benefit, i.e., inferential analyses will be conducted when data collection has been completed. However, primary outcome data will be summarized quarterly and presented to the SO to decide if an interim inferential analysis is warranted to determine whether the study should be terminated early due to relevant benefit.

Table 1. Study Risk Assessment *				SCORE
I. Experimental Treatment				

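### Section 5.2 defines active suicidal ideation, schizophrenia and bipolar disorder by being in treatment, so read literally it does not exclude untreated cases unless untreated depression or substance abuse is also present

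*Combined protocol and SAP*

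**What the plan says.** Section 5.2, patient exclusion 4, opens with the headline "Active schizophrenia, major depressive disorder, bipolar disorder, suicidal ideations, or substance abuse by self-report or chart review". A parenthesis then defines the word that governs the list.

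- For three conditions, running on into depression: "Active means currently being treated for schizophrenia, bipolar disorder, or suicidal ideations or having active and untreated major depressive disorder".
- For depression in full: "having active and untreated major depressive disorder, i.e. not under the care of a clinician", with a further alternative about not being on medication.
- For substance use: "having active and untreated substance abuse, i.e. not on medication or enrolled in a substance abuse program".

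Caregiver exclusion 2 carries the same definition. Its header appears twice. The first time it reads "Active schizophrenia, major depressive disorder, bipolar disorder, suicidal ideation, or substance abuse by self-report" and goes straight into a parenthesis. The second time, inside that parenthesis, chart review is added as a source.

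Suicidal ideation is also mentioned in Section 2.2.3, where the PI is told at once if any participant "expresses suicidal ideation to the nurse coach or study coordinator", and in Section 10.1.7, which begins "If a participant exhibits suicidal ideation at any point" and goes on to a crisis plan.

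**The concern.** One sentence defines one word in two opposite directions. For depression and substance abuse, lack of treatment makes the condition active and so excludes. For suicidal ideation, schizophrenia and bipolar disorder, receiving treatment does so. A coordinator who follows the definition would turn away someone in care for suicidal ideation, and would have no ground in this criterion to turn away someone who discloses ideation on the screening call but is not in care. That is at odds with a headline that lists suicidal ideation among the exclusions.

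The criterion is there to protect participants. Section 2.2.1 names distress from the surveys and sessions as the first risk of taking part. Distress screening takes place at the start of coaching sessions (Sections 2.2.3 and 6.1.1), which only the intervention arm receives. In usual care, 15 of the 30 dyads under Section 6.1.2, Table 1 of Section 6.1.3 schedules study contact only at weeks 1, 12 and 24. For that half, distress screening in sessions cannot make up for an entry screen that works differently from its headline.

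**Working it through.** No arithmetic applies and the plan states no figure to reproduce. The check is to read the criterion as logic and then look for another rule that closes the gap.

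**Step 1. Write out the rule.** Let T mean in treatment for the condition named. Under the parenthesis, a person is excluded if:

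(schizophrenia and T) or (bipolar disorder and T) or (suicidal ideation and T) or (major depressive disorder and not T) or (substance abuse and not T).

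**Step 2. Tabulate each condition taken alone.**

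| Condition | In treatment | Not in treatment |
|---|---|---|
| Schizophrenia | excluded | not excluded |
| Bipolar disorder | excluded | not excluded |
| Suicidal ideation | excluded | not excluded |
| Major depressive disorder | not excluded | excluded |
| Substance abuse | not excluded | excluded |

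Of the 5 × 2 = 10 cells, five are excluded and five are not. Two of the five that are not excluded (treated depression, treated substance abuse) are plainly what the text intends and are not in question. The other three, the untreated cells in the first three rows, are the problem.

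**Step 3. Allow for combinations.** The limbs are joined by *or*. Someone with untreated suicidal ideation who also has untreated major depression or untreated substance abuse is excluded through that second condition. The gap is therefore limited to people with one of the first three conditions, untreated, and neither of those two.

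**Step 4. Look for another rule.**

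- The other patient exclusions in Section 5.2 concern telephone access, recent hospitalization or exacerbation, advanced cancer, hearing and cognition. The other caregiver exclusions concern telephone access, hearing and cognition. None covers these conditions.
- Section 5.4 gives two reasons for screen failure: baseline measures not completed in time, and death before they are completed. Neither applies.
- Section 2.2.3 says what follows a failed cognitive screen: the person is ineligible, and the PI, patient and primary clinician are told. It gives no matching step for suicidal ideation disclosed at screening.
- The texts on suicidal ideation in Sections 2.2.3 and 10.1.7 prescribe notification, risk assessment, referral or a crisis plan. Neither makes anyone ineligible.

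The gap stays open, and since the caregiver definition is the same, the result is the same for caregivers.

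**The case against.** The strongest reply is that staff would give *active* its ordinary meaning and that the protocol has other safeguards. Suicidal ideation voiced to a coach or coordinator goes to the PI at once, with emergency psychiatric referral as back-up. Coaching sessions open with distress screening. Section 7.2 lets the PI withdraw a participant when continued follow-up is not in that person's interest. Section 2.2.1 calls the distress risk quite low. The life-review and legacy sessions (5 and 6) are for patients in the intervention arm only, 15 people as planned. All of this is true and limits the consequences. None of it changes who is eligible. The protocol replaced the ordinary meaning of the word with a definition of its own, and Section 10.1.11 counts noncompliance with the protocol as a deviation, so quietly applying a different meaning is not a clean solution.

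Four stronger readings are tempting, and the documents do not support them.

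- *The definition contradicts Sections 2.2.3 and 10.1.7.* It does not. Those sections manage ideation that arises during participation and set no eligibility rule. The inconsistency lies wholly within Section 5.2.
- *The screen stops only people already in care.* It also excludes untreated depression and untreated substance abuse.
- *The reasons-for-exclusion counts in the Reach outcome would be wrong.* Counts made under the written rule are correct for that rule, and no effect on the outcome can be shown.
- *A single such enrolment would be a safety event.* Nothing in Sections 8.3 or 8.4 defines it as one.

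Section 12.2, the Emotional Distress/Suicide Protocol, is cited but was not in the text available. The places that cite it concern distress or ideation during participation, not eligibility.

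**Conclusion.** The point stands as a defect in the wording of a participant-protection criterion, and it should be corrected. Taken literally, both criteria fail to exclude untreated suicidal ideation, schizophrenia or bipolar disorder in anyone without untreated depression or untreated substance abuse, and they exclude people in treatment for the first three. That is three of five conditions, in two criteria.

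How many people this touches is unknown. The documents give no prevalence and no number to be screened, and the planned 60 participants are an enrolment target, not a count of people screened. The finding has no bearing on sample size, significance level, power or analysis.

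It rests on two assumptions: that the parenthesis governs the headline, as its wording says, and that being in treatment refers to the condition named. It does not assume that anyone with these conditions has been enrolled.

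**What to change.** In patient exclusion 4 and caregiver exclusion 2, the investigators should reconcile the headline with the parenthetical definition so that the text states, for each of the five conditions, whether a treated person is eligible and whether an untreated person is. The table under the working can serve as a template. The choice of clinical rule belongs to the investigators, and this review proposes none. The screening script should be changed to match.

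In caregiver exclusion 2, delete the duplicated header and reconcile the two stated sources, self-report alone and self-report or chart review, so that one rule remains.

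The cost is a text edit to two criteria and the script, plus the IRB approval that the protocol requires before an amendment takes effect. No change to the sample size or the analysis is needed.

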5.3 LIFESTYLE CONSIDERATIONS

N/A

5.4 SCREEN FAILURES

Screen failures are defined as participants who consent to participate in this study but are not subsequently randomized. Reasons for screen failure include:

- 1) Failure of the patient and/or the caregiver to complete baseline measures within 14 days of signing informed consent.
- 2) Death of the patient and/or caregiver prior to completing baseline measures.

5.5 STRATEGIES FOR RECRUITMENT AND RETENTION

Duration of Humans Subjects Involvement: Participant enrollment will begin in study year 2 (Tentatively: June 2022) and last until the study year 4 (Tentatively: June 2024). Some participant activity may extend into study year 5 depending on recruitment.

[figure not shown]
Length of Active Enrollment: We will recruit 2 dyads per month during study years 2 through 4 (2022-2024), to reach our target sample size of 30 dyads by study year 4.

Loss to Follow-Up: We are considering an estimated 20% attrition rate based on the nature of serious illness and have accounted for this loss to follow up by inflating the sample size from 24 to 30 patient participants.

Referral Sources and Estimated Enrollment Rate. The study population will be recruited from the pulmonary clinics at The Kirklin Clinic (UAB). Depending on recruitment goals, we may also include recruitment from Cooper Green Mercy Health Services (UAB Health Authority). We aim to recruit 30 dyads over 3 years. The UAB Pulmonary program saw nearly 800 older adults with COPD in 2018. Our benchmark is 2 dyads per month

Recruitment and Enrollment Procedures. Study staff identify potential patients and their caregivers with a COPD diagnosis in the electronic medical record (UAB IMPACT system; after gaining HIPAA waiver) who have a planned office visit at study recruitment sites in the next 1-2 weeks. After gaining opt out permission from the patient's attending pulmonologist, the study coordinator calls the patient at home. The coordinator informs the patient about the study, answers any questions, invites those interested and eligible to participate, and asks permission from the patient to present the study to the caregiver. Patients and their caregivers (with permission) are screened at this time for eligibility, and agreeable and eligible patients and caregivers complete consent.

Figure. Flow diagram of study procedures.

Procedures to Monitor Enrollment and Track and Retain Participants. The study coordinator who is based at UAB, will prepare weekly enrollment reports that are reviewed at weekly team meetings. The reports will summarize the number of patients and caregivers identified, screened, and enrolled.

Strategies to Promote Retention. Numerous retention strategies are being used to maximize participant intervention and questionnaire completion rates, consistent with best practices:

- Participants will each receive remuneration for each survey assessment completed: \$40 for baseline, \$50 for 12 weeks, \$60 for 24 weeks. Participants will also receive \$50 for completing a post-trial feedback session and \$25 for completing a post-supportive care clinic visit feedback survey for those who complete that visit.
- Use of a trained, experienced study coordinator at UAB who has familiarity with the university, a PI with established relationships with the pulmonologists and their staff, a study team with training in cultural sensitivity and who follow study-team developed recruitment scripts, and who have prior experience recruiting from the cancer population.
- Telephone-based intervention delivery, allowing for flexible scheduling with participants at a day and time that maximizes convenience.
- Participants will be mailed a welcome letter with information about UAB and resources.
- Because lag time between study activities can result in participants not remembering what they have been asked to do for the study, protocol windows consistent with our prior studies will be instituted to ensure timely contact between steps in the procedures.

Contingency Plans. Our pulmonary clinics at UAB see on average 800 adults who are 60 years or older with COPD each year and could potentially meet eligibility criteria. This is sufficiently large enough to target our goal recruitment. If enrollment falls significantly below the accrual benchmarks, defined as less than 2 participants per month, we will consult with the Recruitment and Retention Shared Facility of the UAB Division of Preventive Medicine to identify alternative strategies. These may include face-to-face recruitment by the study coordinator or expansion to include primary care clinics at UAB and Cooper Green Mercy Health Services (UAB Health Authority).

Potential Study-Related Barriers. We have identified that attendance at a separate palliative care clinic visit may be burdensome for some older adults with COPD due to transportation needs, mobility issues, supplemental oxygen, and severe dyspnea. We also identified that some electronic We will continue to explore this barrier in the current study and consider switch to telehealth visits. Our qualitative data reveal that the telephone delivery model of the EPIC intervention resonates with older adults from rural and underserved areas where COPD is prevalent, that the weekly phone calls are not burdensome, and that completion of all patient and caregiver telephone sessions is feasible.

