1.2 SCHEMA: HYBRID TYPE-1, EFFECTIVENESS-IMPLEMENTATION PILOT RANDOMIZED CONTROLLED TRIAL

1.3 STUDY TIMELINE

Key Targets	Pre-Award	Year 1		Year 2		Year 3	Year 4		Year 5	
	-2020	(Sept 2020 - May 2021)		(June 2021 - May 2022)		(June 2022 - May 2023)	(June 2023 - May 2024)		(June 2024 - May 2025)	
IRB approval and registration										
Database preparation										
Focus groups, thematic analysis, qualitative manuscript (Aim 1), trial protocol manuscript										
Coach training, intervention mapping, refine EPIC, print materials, prepare for trial (REDCap, IRB, clinical trials.gov, etc)										
Trial recruitment (2 dyads/month)										
R01 development and submission										1 st Submit Feb 2024
Data analysis publish trial manuscripts										
Implementation of R01										

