9.2 SAMPLE SIZE DETERMINATION

As this is a feasibility study, sample size is justified based on the measurement precision of LSA parameters for a larger study. Using a sample size of 24 patients (48 participants including patients and caregivers) and 12 patients per study arms, we can estimate the 95% confidence interval of mean LSA with a margin of error of 14.3. This margin of error is equal to 0.567 standard deviation when we observe a reference standard deviation for the LSA of 25.2 from a general population of older adults. This sample size also includes an estimated 20% attrition rate from a sample of 30 dyads (or 60 patient and caregiver participants), which is consistent with palliative care trials.

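### The recruitment trigger is in participants and the benchmark in dyads, and the 2-dyad benchmark fits neither stated accrual period

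*Combined protocol and SAP*

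**What the plan says.** **Benchmark.** The timeline in section 1.3 has the row "Trial recruitment (2 dyads/month" and section 5.5 repeats it: "Our benchmark is 2 dyads per month". Section 5.5 also ties the rate to the target: "We will recruit 2 dyads per month during study years 2 through 4 (2022-2024), to reach our target sample size of 30 dyads".

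**Accrual period.** Section 5.5 describes it in three ways:
- by date: "Participant enrollment will begin in study year 2 (Tentatively: June 2022) and last until the study year 4 (Tentatively: June 2024";
- by study year: years 2 through 4, labelled 2022-2024;
- by length: "We aim to recruit 30 dyads over 3 years".

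Section 1.3 dates study year 2 as "June 2021 - May 2022".

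**Trigger.** The contingency paragraph of 5.5 calls for a consultation with the recruitment shared facility "If enrollment falls significantly below the accrual benchmarks, defined as less than 2 participants per month".

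**Unit.** Section 9.2 counts both members of a dyad, describing the loss to attrition as "from a sample of 30 dyads (or 60 patient and caregiver participants". Section 5.5, on loss to follow-up, writes of patient participants when it means patients alone.

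**The concern.** A benchmark in dyads and a trigger in participants can be compared only if the second unit is defined, and in the contingency paragraph it is not. Under one definition the trigger lies at half the benchmark; under the other it coincides with it. Two people running the trial could therefore act at rates that differ by a factor of two.

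The benchmark also does not follow from the target and either stated period, so a team enrolling exactly on schedule for 30 dyads would be reported as well behind it.

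This matters somewhat more here than in most pilots. Recruitment feasibility is part of the primary outcome under Aim 2 (Hypothesis 2, section 9.1), and the Reach row in section 3 lists enrolment rates without a threshold. The target of 30 and the rate of 2 dyads per month are the recruitment figures that a reader of the results will reach for.

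**Working it through.** **Inputs.** Target 30 dyads (5.5, 9.2); benchmark 2 dyads per month (1.3, 5.5); trigger below 2 participants per month (5.5); 20% attrition (5.5, 9.2); LSA standard deviation 25.2 with 12 patients per arm (9.2). The period is 24 months from June 2022 to June 2024 (25 if both end months count), or 36 months for 3 years.

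**The plan's own figures.** Inflation for attrition: 24 / 0.8 = 30, which reproduces. Margin of error: 1.96 × 25.2 / √12 = 14.26, which reproduces the stated 14.3. The target is sound; the accrual figures are what fail to agree.

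**Benchmark against period.** Time needed at the benchmark: 30 / 2 = 15 months.

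| Period | Dyads at 2 per month | Rate needed for 30 dyads | Dyads at 1 per month |
|---|---|---|---|
| 24 months | 48 | 30/24 = 1.25 per month | 24 |
| 25 months | 50 | 30/25 = 1.20 per month | 25 |
| 36 months | 72 | 30/36 = 0.83 per month | 36 |

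No stated period gives 30 dyads at 2 per month. A team that enrolled 30 in 24 months would meet the target and still be 1 − 1.25/2 = 37.5% below the benchmark.

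**Trigger, participants counted as in 9.2.** 60 participants / 30 dyads = 2 per dyad, so 2 participants = 1 dyad per month, half the benchmark. Accrual at exactly that rate is not below the trigger. It falls 6 dyads short over 24 months, 5 short over 25, and exceeds the target by 6 over 36. The break-even period is 30 / 1 = 30 months. Over 24 months, rates from 1.0 to just under 1.25 dyads per month miss 30 without setting off the trigger; over 36 months no such rate exists. If accrual is assumed to be Poisson with mean 1 dyad per month, the chance of reaching 30 is 0.13 at 24 months, 0.18 at 25 and 0.86 at 36.

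**Trigger, participants meaning patients.** 2 patients = 2 dyads per month. The trigger equals the benchmark, and any rate under 2 counts as significantly below it, including the 1.25 that delivers 30 dyads in 24 months.

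**Calendar.** By section 1.3, June 2022 opens year 3 and June 2024 opens year 5, whereas 5.5 places them in years 2 and 4. Years 2 through 4 of section 1.3 run from June 2021 to May 2024, which is 36 months but starts a year before the stated first enrolment. Thirty-six months counted from June 2022 would end in May 2025, the last month of the timeline, with no time left for the final dyads' 24-week follow-up.

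**Worst-case size.** 24 dyads × 0.8 = 19.2, or 9.6 per arm; 1.96 × 25.2 / √9.6 = 15.9, against 14.3. The ratio is √(12/9.6) = 1.12, so the margin is about 12% wider.

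**The case against.** Four objections deserve weight.

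- **The unit may be patients.** The sentences just before the trigger count only older adults with COPD, and 5.5 gives its inflated target in patients. On that reading the trigger is not half of anything. This stands, so a reader who infers flatly that the trigger is half the benchmark goes further than the text allows. The text still needs correcting, because the trigger then makes no distinction between any shortfall and a significant one.
- **A rescue threshold may properly lie below the goal, and a benchmark may include slack.** Both are reasonable designs. The text states neither, and presents 2 dyads per month over years 2 through 4 as the route to 30.
- **A shortfall would be seen anyway.** The coordinator's enrolment reports go to the team every week (5.5), the oversight committee reviews milestones twice a year (10.1.6), and 5.5 already allows recruitment at the second clinic. This stands: the trigger governs one consultation, and an inference that poor accrual would pass unnoticed is not supported.
- **The window is tentative.** Both dates are so labelled, and 5.5 lets some participant activity run into year 5 depending on recruitment. The recruitment bars in 1.3 and a figure in 5.5 were not readable in the text reviewed and may show the intended window. This limits the claim about missing 30, but the written figures still disagree.

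**Conclusion.** The accrual figures in 1.3 and 5.5 need to be reconciled. One part holds on every reading: 2 dyads per month reaches 30 in 15 months and fits neither the 24 to 25 months given by the dates nor the 3 years given in words.

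The rest is conditional. That the trigger is half the benchmark rests on counting participants as section 9.2 does. That it stays silent at a rate missing 30 rests on that count and on the June 2022 to June 2024 window; it fails over 3 years, where the same rate gives 36 dyads. A reader might also infer that a trial below 2 dyads per month has failed Hypothesis 2. No section makes that rate a success criterion, so the documents do not support this.

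The impact is mainly operational. No estimand or analysis changes, and in the worst case considered the LSA margin moves from 14.3 to about 15.9 in a pilot whose LSA aim is descriptive. The correction is still worth making, because it concerns a decision threshold in a trial where recruitment feasibility is a primary outcome.

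**What to change.** 1. State one accrual window in calendar dates that agree with the study years in 1.3, and remove the competing descriptions from 5.5.
2. Give the required rate as 30 divided by that window: 1.25 dyads per month for 24 months, or 0.83 for 36.
3. Either set the benchmark to that rate, or keep 2 dyads per month and say that it includes deliberate slack.
4. Write the contingency trigger in randomised dyads, preferably as cumulative accrual against the required line, and state how many dyads behind the line counts as significant. A short rolling window is a poor choice. For example, with Poisson accrual at exactly 1.25 dyads per month, 3 months has mean 3.75, and the chance of 3 or fewer dyads, which is a mean rate below 1.25, is about 48%.
5. Use the same figures in 1.3, in 5.5 and when reporting recruitment under Hypothesis 2.

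The cost is wording only, with no change to design or sample size. The practical downside is that the recruitment facility may be consulted earlier.
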